## 9.2 Adverse Events

Adverse events (AEs) will be summarized and presented using primary MedDRA System Organ Classes (SOCs) and preferred terms (PTs) according to the version of the MedDRA coding dictionary used for the study at the time of database lock. The actual version of the MedDRA coding dictionary used will be noted in the AE tables and in the clinical study report. Specific adverse events will be counted once for each subject for calculating percentages, unless stated otherwise. In addition, if the same adverse event occurs multiple times within a subject, the highest severity and level of relationship to investigational product will be reported.

## 9.2.1 Treatment-Emergent Adverse Events

Treatment-emergent adverse events (TEAEs) for each safety population are defined as follows:

# **TEAEs during the 12-month placebo-controlled Treatment Period on Safety Analysis Set during the placebo-controlled Treatment Period**

TEAEs during the 12-month placebo-controlled Treatment Period are defined as any AEs with the onset that is on or after the first dose of study drug during the 12-month placebocontrolled Treatment Period and no more than 30 days after the last dose of study drug for subjects who premature discontinue during the 12-month double-blind Treatment Period or until the first dose of study drug in the open-label Treatment Period for subjects who enter the open-label Treatment Period. AEs starting more than 30 days following discontinuation of study drug will not be included in summaries of treatment-emergent AEs but will be summarized separately.

# TEAEs during the open-label Treatment Period on the Safety Analysis Set during the open-label Treatment Period

TEAEs during the open-label Treatment Period are defined as any AEs with the onset that is on or after the first dose of study drug during the open-label Treatment Period and no

more than 30 days after the last dose of study drug in the study. AEs starting more than 30 days following discontinuation of study drug will not be included in summaries of treatment-emergent AEs but will be summarized separately.

TEAEs for All Elagolix plus E2/NETA Analysis Set

TEAEs for All Elagolix plus E2/NETA Analysis Set are defined as any AEs with the onset that is on or after the first dose of elagolix plus E2/NETA (either in the placebocontrolled Treatment Period or open-label Treatment Period) and no more than 30 days after last dose of elagolix plus E2/NETA. AEs starting more than 30 days following discontinuation of study drug will not be included in summaries of treatment-emergent AEs but will be summarized separately.

The number and percentage of subjects experiencing treatment-emergent AEs will be summarized overall, as well as by primary MedDRA SOC and PT by treatment group. The SOCs will be presented in alphabetical order, and the PTs will be presented in alphabetical order within each SOC.

## 9.2.2 Adverse Event Overview

An overview of treatment-emergent AEs will be presented consisting of the number and percentage of subjects experiencing at least one event for each of the following AE categories:

- Any treatment-emergent AE
- Any treatment-emergent AE related to study drug according to the investigator
- Any severe treatment-emergent AE
- Any serious treatment-emergent AE
- Any treatment-emergent AE leading to discontinuation of study drug
- Any treatment-emergent AE leading to death
- Any treatment-emergent AE of special interest as specified in Appendix A
- All deaths

## 9.2.3 Treatment-Emergent Adverse Events by SOC and PT

Treatment-emergent adverse events will be summarized by SOC and PT; by maximum relationship to study drug as assessed by the investigator (e.g., reasonable possibility) and SOC and PT; by maximum severity and SOC and PT; and by subject number and SOC and PT. Specific adverse events will be counted once for each subject for calculating percentages, unless stated otherwise. In addition, if the same adverse event occurs multiple times within a subject, the highest severity and level of relationship to investigational product will be reported.

In addition, treatment-emergent adverse events will be summarized by PT and sorted by decreasing frequency for the elagolix plus E2/NETA group.

## 9.2.4 Treatment-Emergent Adverse Events per Patient-Years of Exposure

An overview of AEs for All Elagolix plus E2/NETA Analysis Set will be presented per 100 patient-years. In addition, TEAEs for All Elagolix plus E2/NETA Analysis Set will be presented per 100 patient-years by SOC and PT. AEs per 100 patient-years of exposure are defined as the number of AEs divided by the total exposure in 100 patient-years. Note that one event per preferred term per day per subject will be counted in the calculation of the number of AEs (i.e., a preferred term will not be counted twice on the same day for the same subject).

TEAEs per 100 patient-years of exposure = 
$$100 \times \frac{\text{Number of TEAEs}}{\text{Total Patient Years}}$$

where total patient years are defined as the sum of the study drug exposure (defined as date of last dose of elagolix plus E2/NETA – date of first dose of elagolix plus E2/NETA + 30 days) of all subjects normalized by 365.25, and rounded to one decimal place.

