#### **Phase 3 Clinical Development Program for Uterine Fibroids**

The overall objective of the Phase 3 registration clinical development program is to generate requisite safety, tolerability, and efficacy data in 2 replicate 6-month Phase 3 pivotal studies and 1 safety and efficacy extension study (total 12-month treatment period) to support use of elagolix 300 mg BID with E2/NETA (estradiol 1.0 mg/norethindrone acetate 0.5 mg) for the intended indication of the chronic management of HMB associated with uterine fibroids.

The primary objective of this current Phase 3b (Study M16-283) study in women with HMB associated with uterine fibroids is to obtain extended data on the safety of elagolix 300 mg BID with standard dose E2/NETA. All subjects will have the opportunity to be treated with elagolix 300 mg BID with standard dose E2/NETA for the second, third and fourth years of the study enabling a careful examination of the long term safety of this dose over 48 months, particularly with respect to bone loss compared to baseline.

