## 8.2 Determination of Sample Size

Approximately 500 subjects will be randomized (2:1) to elagolix 300 mg BID plus E2/NETA (N = 335) and placebo (N = 165).

Based on clinical review, a sample size of 500 was selected to gather long term safety exposure data in approximately 50 subjects completing 48 months of study drug dosing, with approximately 30 subjects receiving 48 months of active drug elagolix 300 mg BID plus E2/NETA 1/0.5 mg QD.

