## 2.4 Sample Size Determination

Approximately 500 subjects will be randomily assigned (2:1) to elagolix 300 mg BID plus E2/NETA (N = 333) and placebo (N = 167).

Based on clinical review, a sample size of 500 was selected to gather long term safety exposure data in approximately 50 subjects completing 48 months of study drug dosing, with approximately 30 subjects receiving 48 months of active drug elagolix 300 mg BID plus E2/NETA 1/0.5 mg QD.

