#### All Elagolix plus E2/NETA Analysis Set:

For subjects who received at least 1 dose of elagolix plus E2/NETA (either in the placebocontrolled or open-label Treatment Period), the duration of treatment is defined as the last dose date of receiving elagolix plus E2/NETA minus the first dose date of receiving elagolix plus E2/NETA plus 1 day.

In addition, the number and percentage of subjects in each treatment duration interval  $(1 - < 84 \text{ days}, 84 - < 168 \text{ days}, 168 - < 252 \text{ days}, 252 - < 336 \text{ days}, 336 - < 420 \text{ days}, 420 - < 504 \text{ days}, 504 - < 588 \text{ days}, 588 - < 672 \text{ days}, 672 - < 756 \text{ days}, 756 - < 840 \text{ days}, 840 - < 924 \text{ days}, 924 - < 1008 \text{ days}, 1008 - < 1092 \text{ days}, 1092 - < 1176 \text{ days}, 1176 - < 1260 \text{ days}, 1260 - < 1344 \text{ days}, \ge 1344 \text{ days})$  will be summarized.

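### Adverse event rates per 100 patient-years are not split by time on elagolix, so a doubling confined to the fourth 12 months would raise the overall rate by only about 6-11%

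*SAP*

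**What the plan says.** SAP 9.2.4 defines the rate for the All Elagolix plus E2/NETA set: "AEs per 100 patient-years of exposure are defined as the number of AEs divided by the total exposure in 100 patient-years". Each woman's exposure runs from first to last elagolix dose with 30 days added, divided by 365.25. The rate is given for the AE overview and by SOC and preferred term. A preferred term counts at most once a day in any woman, so recurrences are counted. No time interval is defined.

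SAP 4.0 presents this set by the treatment received at randomisation, so the default is one column per randomised arm. Whether a combined column is added is not stated.

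The other AE tables (SAP 9.1 and 9.2.1 to 9.2.6) give numbers and percentages of subjects. They are produced separately for the placebo-controlled period, the open-label period and the all-elagolix set. The open-label tables take Months 13-48 together. Protocol 8.1.1 keeps continuers and placebo switchers in separate groups there. SAP 2.6 allows analyses at Months 24, 36 and 48 but does not require them, and defines no interval rates.

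SAP 6.0 does break exposure in the all-elagolix set down by time on drug, giving "the number and percentage of subjects in each treatment duration interval" up to 1344 days and beyond. Events are never broken down the same way.

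On retention, SAP 2.4 plans for "approximately 50 subjects completing 48 months of study drug dosing", of whom "approximately 30 subjects receiving 48 months of active drug". The Protocol's account of the Phase 3 programme describes all women being offered active treatment in Years 2-4 as "enabling a careful examination of the long term safety of this dose over 48 months", particularly for bone loss.

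**The concern.** One rate over all time on drug describes the whole period only if the event rate is constant over that time. The SAP neither states nor checks this. If about 90% of women stop before Month 48, the denominator is mostly early exposure, and the rate mainly describes the first two 12-month blocks.

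Two patterns would then be hard to see. A harm that emerges late is diluted by the earlier exposure. SAP Appendix A lists fracture, thromboembolic events and hormonally mediated malignancies, whose risk might change with duration. Conversely, an early transient effect such as hot flush is averaged down towards a low, apparently constant rate. The table would also not show how little fourth-year evidence stands behind it.

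**Working it through.** **Inputs.**
- Randomised: 333 and 167 (SAP 2.4). Protocol 8.2 has 335 and 165; the shares below agree to within about 0.1 percentage point either way.
- Completing 48 months: about 50, of whom about 30 have 48 months on active drug (SAP 2.4). By subtraction, about 20 come from the placebo arm.
- A month is 28 days (Protocol 1.3), so 12 months = 336 days and 48 months = 1344 days.
- Placebo switchers start elagolix at about day 336. They reach at most 36 months on drug and add no dosing time to the fourth block.

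**The plan's own figures.** A 2:1 split of 500 gives 333.3 and 166.7, which matches the SAP. Implied retention is 50/500 = 10% overall, 30/333 = 9.0% and 20/167 = 12.0%. The sample size rests on clinical review, with no formula or dropout rate, so there is nothing further to reproduce.

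**Assumed dropout.** Retention is stated only at Month 48, so the curve between is an assumption. Two families were used:
- Weibull, N(t) = N0 × exp(−λ t^k), with λ set so that N(1344) is 30 or 20, and k from 0.5 to 2
- straight-line loss from N0 to 30 or 20

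Patient-years in a block are the area under N(t) divided by 365.25.

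**Worked case, constant hazard (k = 1).** For the elagolix arm:
- λ = ln(333/30)/1344 = 0.001791 per day and N(1008) = 54.8
- fourth block = (54.8 − 30)/0.001791/365.25 ≈ 37.9 patient-years
- whole arm = (333 − 30)/0.001791/365.25 ≈ 463.2 patient-years
- share = 37.9/463.2 = 8.2%

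Switchers add 70.1 + 41.3 + 24.3 = 135.7 patient-years in their first three blocks. The total is about 599, and the pooled share is 37.9/598.9 = 6.3%.

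| Dropout curve | Fourth block, patient-years | Elagolix arm total | Share, elagolix arm | Both arms total | Share, both arms |
|---|---|---|---|---|---|
| Weibull 0.5 | 32.4 | 293.2 | 11.1% | 385.8 | 8.4% |
| Weibull 0.6 | 33.5 | 330.9 | 10.1% | 432.0 | 7.8% |
| Weibull 1.0 | 37.9 | 463.2 | 8.2% | 598.9 | 6.3% |
| Weibull 1.5 | 43.8 | 588.3 | 7.4% | 764.9 | 5.7% |
| Weibull 2.0 | 50.1 | 680.2 | 7.4% | 892.2 | 5.6% |
| Linear | 62.4 | 667.9 | 9.3% | 875.2 | 7.1% |

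The first two blocks supply about 74-78% of the pooled exposure and 71-77% of the elagolix arm's.

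**Added 30 days.** Including them gives a pooled share of 6.0-6.7% (constant hazard) or 6.8-7.8% (linear), depending on the block to which the added days are assigned.

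**Effect on the rate.** If the rate is multiplied by R in the fourth block only, the overall rate is multiplied by 1 + (R − 1) × share.
- R = 2: a rise of 5.6% to 11.1%.
- R = 3: a rise of 11.2% to 22.2%.
- An event confined to that block appears in the overall rate at about 1/18 to 1/9 of its rate there.

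**Limits of the assumption.** Step patterns fall outside the pooled range: about 2% if all losses come just before Month 36, 17% if all come on Day 1, and 18% if all come just before Month 48. These are contrived, but the documents do not exclude them.

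**Precision in the last block.** With zero events in 38 patient-years, the one-sided 95% upper bound is 3/38 = 7.9 per 100 patient-years. The upper limit of an exact two-sided 95% interval is 3.69/38 = 9.7.

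**The case against.** Two stronger readings are tempting, and the documents support neither.
- A reader might infer that the open-label AE tables mix women in their first year on elagolix with women in their second. Protocol 8.1.1 requires separate summaries for continuers and switchers, and SAP 2.3 and 9.2.1 present data by treatment group.
- A reader might infer that each preferred term gets a single rate across both arms. SAP 4.0 makes randomised-arm columns the default. Switchers only dilute a combined column, so the elagolix-arm share of 7-11% is the fairer headline.

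Several mitigations are also real. For continuers, the two period tables already separate days 1-336 from later, so an early transient effect shows in the first. In the continuers' open-label table the fourth block is about 13-22% of exposure under the curves above. Serious AEs, deaths and AEs leading to discontinuation are listed by subject. BMD, endometrial findings, laboratory data and C-SSRS are summarised by visit. The formal 48-month objective is BMD; the other objective is safety against placebo at 12 months.

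These points narrow the concern but do not remove it. The period tables give percentages, which ignore unequal follow-up, and they leave Months 13-48 as one block. Listings show cases without a denominator. For AEs outside the visit-based measures, no planned table shows whether the rate changes with time on drug.

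It is also fair to object that late intervals will be imprecise and will hold only women who stayed on drug. Both limits must be stated beside the table. Neither is avoided by pooling, which only hides them.

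**Conclusion.** The point holds as a cheap improvement, not as an error. The overall rate in SAP 9.2.4 is valid as an average over time on elagolix, but it cannot show change with duration, and no other planned AE table gives exposure-adjusted rates by time on drug. With the plan's Month 48 retention and smooth or linear dropout, the fourth 336-day block supplies about 32-62 patient-years: about 7-11% of elagolix time in the elagolix-randomised arm, or about 6-8% with both arms pooled. A doubling confined to that block raises the overall rate by about 6-11%.

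The size rests on the assumed shape of dropout and on the placebo-arm completers obtained by subtraction. The absence of a time split does not depend on either. The point concerns AE rates only, not BMD.

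**What to change.** In SAP 9.2.4, keep the overall rate. For the All Elagolix plus E2/NETA set, add subjects with events, events, patient-years and the rate per 100 patient-years by time since first elagolix dose: days 1-336, 337-672, 673-1008 and after 1008. Show these by randomised arm and in total. Limit them to the AE overview, serious AEs, AEs leading to discontinuation and the Appendix A AESI groups.

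Give exact Poisson 95% limits for first-event rates, with exposure censored at the first event. If recurrent events are counted, as 9.2.4 now does, use limits that allow for clustering within subjects, because plain Poisson limits can be too narrow.

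State two cautions with the table. Limits in the last interval will be wide, as the zero-event calculation shows. Late intervals contain only women who stayed on drug, so a falling rate may reflect selection and not lower risk.

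The cost is SAP wording and one set of tables. The planned analyses already need the onset and dosing dates, so no new data are required.

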#### 6.1.4 Adverse Event Collection Period

All adverse events reported from the time of study drug administration until 30 days following discontinuation of study drug administration have elapsed will be collected, whether solicited or spontaneously reported by the subject. All nonserious adverse events of bone fracture, clinically significant BMD loss, or newly diagnosed medically-related bone condition will be collected during the Post-Treatment Follow-Up Period, until the subject discontinues from study participation. In addition, serious adverse events and protocol-related nonserious adverse events will be collected from the time the subject signed the study-specific informed consent.

Adverse event information will be collected as shown in Figure 4.

[figure not shown]
[figure not shown]

Figure 4. Adverse Event Collection

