## 2.5 End of 12-Month Placebo-Controlled Treatment Period Analysis

An end-of-placebo-controlled treatment period analysis will be performed after the last subject completes the 12-Month placebo-controlled Treatment Period. These analyses will include data collected during the full Treatment Period (placebo-controlled and openlabel Treatment Periods) and the Follow-Up Period up to the data cut-off for the interim lock. The database will be versioned for an interim lock and any discrepant data will be clarified before the versioning. Analyses will be performed by AbbVie.

Since this end-of-placebo-controlled treatment period analysis is the only and final analysis for the comparison between treatment and placebo group at 12 months of safety and efficacy endpoints, no additional adjustment of alpha-level is necessary.

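### The patient-year denominator adds 30 days with no cap at the data cut-off, so interim adverse event rates are understated for women still on drug

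*SAP*

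**What the plan says.** SAP 9.2.4 defines the rate: "AEs per 100 patient-years of exposure are defined as the number of AEs divided by the total exposure in 100 patient-years". Below the formula it adds: "where total patient years are defined as the sum of the study drug exposure". The per-woman denominator is "date of last dose of elagolix plus E2/NETA – date of first dose of elagolix plus E2/NETA + 30 days", summed over all subjects and converted to years. It makes no exception for women still taking drug.

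The numerator is set in SAP 9.2.1. For the All Elagolix plus E2/NETA set, events count from the first elagolix dose to 30 days after the last, and "AEs starting more than 30 days following discontinuation of study drug will not be included in summaries of treatment-emergent AEs". Protocol 6.1.4 collects events over the same span: "All adverse events reported from the time of study drug administration until 30 days following" the end of dosing.

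SAP 2.5 commits to an analysis once the last subject has completed Month 12. It uses data from both treatment periods and "the Follow-Up Period up to the data cut-off for the interim lock". SAP 2.6 allows, but does not require, further locks at Months 24, 36 and 48.

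For the same set, SAP 6.0 measures treatment duration differently: the last "dose date of receiving elagolix plus E2/NETA minus the first dose date of receiving" the combination, plus 1 day. So the quantity that 9.2.4 calls study drug exposure is not the duration defined in 6.0. It is closer to time at risk.

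**The concern.** The 30 days stand for the off-drug window in which an event still counts as treatment-emergent. A woman who is dosing at the cut-off has not entered that window. The days enlarge her denominator and cannot contribute an event.

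Safety is the purpose of this study, and SAP 4.0 summarises the All Elagolix set by treatment at randomisation. At the Month 12 lock, women who began on placebo have short elagolix exposure and most are still dosing. Their column is therefore diluted more than that of women on elagolix from the start. The dilution also shrinks from one lock to the next, so a rate could appear to rise over time because of the formula alone.

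**Working it through.** The documents state no event rate or patient-year total for this analysis, so there is no figure to reproduce. The check compares the formula's days with the days in which an event can be counted. The event count is the same either way, so the relative error in the rate is countable days / formula days − 1.

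**Inputs from the documents.** Denominator: SAP 9.2.4. Event window: SAP 9.2.1. Month of 28 days: Protocol 1.3, so Month 12 is 336 days and Month 48 is 1344. About 30 of 333 women reach 48 months on active drug: SAP 2.4, which gives a constant discontinuation hazard of ln(333/30)/48 = 0.050 per month.

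**Formula.** Let T = last dose − first dose + 1. SAP 9.2.4 gives every woman (T − 1) + 30 = T + 29 days.

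**Stopped and followed for 30 days.** Countable days are T + 30.
- T = 336: 366/365 − 1 = +0.3%.
- T = 1344: 1374/1373 − 1 = +0.07%.

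The formula is one day short, so the rate is very slightly high.

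**Still dosing, last dose taken as the cut-off.** Countable days are T.

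| T (days) | Person-time overstated, 29/T | Rate contribution, T/(T + 29) − 1 |
|---|---|---|
| 84 | 34.5% | −25.7% |
| 168 | 17.3% | −14.7% |
| 336 | 8.6% | −7.9% |
| 672 | 4.3% | −4.1% |

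At the Month 12 lock, the 84- and 168-day rows can apply only to recent placebo switchers. Women on elagolix from the start who are still dosing have about 336 days or more.

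**Recorded last dose g days before the cut-off.** With T now running to the cut-off, the formula gives T − g + 29 days. At T = 336:
- g = 14: 336/351 − 1 = −4.3%.
- g = 28: 336/337 − 1 = −0.3%.

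**Whole set at the Month 12 lock.** This was simulated with assumed uniform enrolment over 12, 24 or 36 months and constant discontinuation of 0.02 or 0.050 per month. The last dose of ongoing women was set to the cut-off or to 14 days before it.

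| Discontinuation | Enrolment | Overall | Elagolix from start | Placebo switchers | Overall, 14-day gap |
|---|---|---|---|---|---|
| 0.02 | 12 months | −5.8% | −4.5% | −14.0% | −3.1% |
| 0.02 | 24 months | −4.0% | −3.2% | −7.2% | −2.1% |
| 0.02 | 36 months | −3.0% | −2.5% | −4.8% | −1.5% |
| 0.05 | 12 months | −4.4% | −3.3% | −13.1% | −2.3% |
| 0.05 | 24 months | −2.8% | −2.1% | −6.4% | −1.4% |
| 0.05 | 36 months | −1.9% | −1.5% | −4.0% | −1.0% |

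These can be checked by hand. If a share p is still dosing and mean duration is m, countable days average m + 30(1 − p) and formula days m + 29, so the error is (1 − 30p)/(m + 29). In the last row overall, p = 0.30 and m = 393: (1 − 9)/422 = −1.9%. The simulated errors run slightly larger in places because women who stopped less than 30 days before the cut-off are also only partly observed.

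**Later locks, same assumptions, overall, last dose at the cut-off.** Month 24: −0.7% to −2.8%. Month 36: −0.1% to −1.7%. Month 48 and final: +0.1% to +0.2%.

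**The case against.** The strongest defence is that the 30 days belong in the denominator. They match the treatment-emergent window and the collection window. Without them, the rate for women who stopped would be too high by 30/336 = 8.9% at 336 days and 30/1344 = 2.2% at 1344 days. This stands, and the repair must keep them.

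Second, the SAP does not say what last-dose date an ongoing woman receives. Protocol 5.5.6 collects recent dosing at on-site and phone visits, about every 28 days. If the last recorded dose lags the cut-off, the error shrinks and can almost disappear. This also stands, and it is why the size is given as a range.

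Third, the consequences are limited. By default, SAP 9.1 makes no statistical comparison in this set. The placebo-controlled 12-month comparison and all tables of subject counts and percentages do not use the formula. The Month 24 and 36 locks are optional.

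None of this removes the error at the Month 12 lock, which SAP 2.5 says will take place.

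**Conclusion.** The point holds for women still on drug at an interim lock, chiefly the Month 12 lock and, if performed, those at Months 24 and 36. With the last dose at the cut-off, Month 12 rates are understated by about 2% to 6% overall, 1.5% to 4.5% for elagolix from the start and 4% to 14% for placebo switchers. Enrolment time, interim retention and the last-dose rule are assumptions, because the documents do not give them. So is the production of the 9.2.4 table at that lock: SAP 2.5 brings in the open-label data, but no list ties tables to locks.

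A reader might infer that the formula understates adverse event rates throughout the study. The documents do not support that. For women who stopped and were followed, the rate is about 0.3% high at 336 days, and the Month 48 and final analyses are essentially unaffected. Nor does the point touch the comparison with placebo. It is a missing censoring rule of modest size, worth correcting because the correction is easy.

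**What to change.** In SAP 9.2.4, define each woman's time at risk as

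min(last elagolix dose + 30 days, data cut-off, last contact or death) − first elagolix dose + 1

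and use it at every lock. Call it time at risk rather than study drug exposure, so that it is not confused with the duration in SAP 6.0.

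This keeps the 30 days for women who have stopped and restores the missing day (T + 30). For women still dosing it ends time at the cut-off or last contact. It also largely removes dependence on the unstated last-dose rule, because the recorded last dose then matters only if it lies more than 30 days before the cut-off.

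The cost is one SAP sentence and a small code change, with no new data. Interim rates become slightly less favourable.
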